#### F. Statistical Considerations:

**F1. Randomization and blinding:** Patients will be randomized (1:1:1) to one of the three ACT target groups (low, medium, or high) using a dynamic minimization algorithm so as to optimize the likelihood that balance between the low, medium, and high ACT target groups will be

achieved with respect to sex (male or female) and glomerular filtration rate (30 to 59 ml/min/1.73m^2 or ≥60 ml/min/1.73m^2). The algorithm will be implemented in RAVE RTSM, a secure web-based interface, and accessed by the study coordinator or other appointed study personnel. Randomization will be conducted after the diagnostic portion of the procedure on only patients who will require ACT monitoring. Since eligible patients will require ACT monitoring during PCI, we will not conduct the study in a strictly blinded fashion. However, study participants will not be informed of their randomization assignment.

**F2. Data collection and handling:** Electronic case report forms along with a corresponding secure REDCap database will be created for data collection (29). Data to be collected will include baseline demographics, comorbidities, procedural variables, in-hospital events, NACE component, and adverse events.

**F3: Definition of study outcomes:** Study endpoints are summarized in Appendix II.

**F3.1 Primary study endpoint:** Our **primary study endpoint is bleeding** and is defined as either a Bleeding Academic Research Consortium (BARC) hemorrhage grade of 1, 2, 3, or 5 or an EASY hematoma scale grade of I-V from the time of PCI to the time the patient is discharged from the hospital.

**F3.2 Primary safety endpoint:** Our **primary safety endpoint is a composite of net adverse clinical events (NACE) and stent thrombosis**, as defined by the Academic Research Consortium, from the time of PCI to the time the patient is discharged from the hospital.

**F3.2.1 NACE** is the composite of all-cause mortality, myocardial infarction (MI), stroke, target lesion revascularization, and major bleeding within 30 days after PCI.

**F3.2.2 MI** will be defined as any two of the following 3 criteria: 1) chest pain for at least 20 minutes; 2) elevation of cardiac biomarkers, preferably troponin, above the laboratory upper limit of normal; and 3) new pathological Q wave on electrocardiogram.

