**F3.3.3 Stroke** will have occurred if post-PCI neurological symptom is confirmed as a stroke by a consultant neurologist at Mayo Clinic with documentation on appropriate neuroimaging (CT or MRI).

**F3.3.4 Major bleeding** will be defined as BARC grade 3 or 5 or EASY grade ≥III.

**F3.3.5 Target vessel revascularization** will be defined as clinically driven revascularization, either by percutaneous or surgical means.

**F3.3.6 Intra-procedural events** would include both bleeding and thrombotic complications. Intra-procedural thrombus will be defined as a visible filling defect noted by the primary operator on the guiding catheter or intracoronary wire or device on selective angiogram.

**F3.4** The study definition of non-inferiority will be defined based on the 95% confidence interval for the difference in proportions of patients with NACE in the low and high ACT target groups,  $\Delta = p^L - p^H$ , with a lower limit of  $\Delta_L$  and an upper limit of  $\Delta_U$ . Low ACT target will be considered to be non-inferior to high ACT target if one of the following holds, depending on the estimate  $p^H$  :

- $\Delta_U < 0.12$  if  $p^H \geq 0.12$
- $\Delta_U < p^H$  if  $0.04 < p^H < 0.12$
- $\Delta_U < 0.04$  if  $p^H \leq 0.04$

Note that italicized version are the theoretical proportions and the estimates are not italicized.

**F.4. Sample size determination:** Recognizing the limitations of previously performed studies regarding ACT and risk of bleeding, including variability in definitions of bleeding, we estimate that the highest ACT target group will experience the in-hospital primary outcome at a rate of 25%, while the lowest ACT target will experience the in-hospital primary outcome at a rate of 5%. A **sample size of 504 patients** was determined to ensure more than 80% power at the

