two-sided overall 5% significance level with Bonferroni adjustment for multiple testing ( $p$  value  $\leq 0.025$  considered as statistically significant) to detect an absolute difference in in-hospital bleeding (Aim 1) between the low ACT target and the medium ACT target (ie. 5% vs. 15%) in addition to a 20% absolute difference between the low ACT target and the high ACT target (ie. 5% vs. 25%). The power was estimated on the basis of 5000 simulations. Patients meeting eligibility criteria for the study and who consent for participation but that do not undergo randomization due to either not receiving intracoronary diagnostic imaging (IVUS/OCT) or physiologic testing (iFR/FFR) or PCI will be entered into the ACT registry and observed for clinical events, including 30-day outcomes. The reason these patients are not categorized as screen failures is because the final criterion for eligibility is receipt of PCI, a criterion that is not known until the coronary angiogram is performed which is after patients have signed informed consent. Because patients receive moderate sedation during their procedure as part of standard of care, ethical and scientific prudence dictates that informed consent be obtained prior to procedural start. True screen failures, therefore, are those subjects not meeting study inclusion or exclusion criteria. . Based on current lab practice patterns at our institution, it is anticipated that approximately 20% of patients who enroll in the study will not require ACT monitoring after the diagnostic portion of the procedure, therefore we intend to consent up to 780 patients. In 2016, there were 240 PCI procedures and 220 adjunctive coronary imaging/physiology procedures (Fractional Flow Reserve = 158, Intravascular Ultrasound = 59, Optical Coherence Tomography = 12) establishing the feasibility of performing the study and meeting patient accrual targets over an **18 - 24 month period.**

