We also considered the implications of this samples size with the other primary aims. For purposes of estimating the incidence of our study endpoint and safety endpoint (Aim 2), a sample size of 504 with equal allocation to each of the three study arms would produce a two-sided 95% confidence interval with a width of 0.15 or less using the Wilson score method. This sample size would also ensure more than 80% power to show evidence of non-inferiority for our primary safety endpoint (NACE, Aim 3) in patients with a low ACT target compared to those with a high ACT target according to the above criteria (section F3.4) when the low and high ACT targets are the same with respect to NACE assuming the probability of NACE with a high ACT target is 12% or more. A review of the published literature had a median estimated rate of 12% for NACE (range 4% to 20% (Table 2).

Table 2.

Study	Hematoma Rate (%)	Major bleeding Rate (%)	NACE Rate (%)	Mean ACT range (sec)	Comments
Petroglou et al (25)	18	3	NR	147	Mostly diagnostic procedures, all radial cases, 5F sheaths, no high risk patients
Jolly SS (26)	3	3	4	NR	Acute coronary syndrome patients, strict bleeding definitions
Bertrand OF (27)	5	1	20	315	All radial cases

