Baseline patient and procedure characteristics of the three groups will be reported as number and percentage for categorical variables and median and interquartile range for continuous variables. To evaluate the possibility of imbalance, we will make comparisons between the three randomized groups using a Kruskal-Wallis test for ordered or numeric variables and a chi-square test (or Fisher's exact test) for categorical variables. For those baseline characteristics with imbalance between groups, we will summarize the number and percentage as well as relative risk and 95% confidence intervals as was done with the pre-planned analyses of sex, access site, and concomitant use of glycoprotein (GP) IIb/IIIa inhibitors with stratification by the baseline characteristic. In addition, we will use a multivariable logistic regression model with in-hospital bleeding as our outcome measure and fixed effects for group (reference group = low ACT target), sex, access site, concomitant use of glycoprotein (GP) IIb/IIIa inhibitors, and any other baseline characteristics with evidence of potential imbalance between groups (p-value  $\leq 0.20$ ) allowing no more than one variable for every 10 patients who experience in-hospital bleeding.

F5.4 Exploratory analysis plan: We will explore the association of ACT target with individual components of bleeding and NACE using a Cochran-Armitage trend test and report the number and percent of patients with each component separately for each group. Adjustment for multiple testing will be conducted using the Holm step-down method.

F5.5 Interim analysis plan: A blinded review of the study's overall incidence of the primary study outcome and the primary safety endpoint will be planned after 50% of patients have completed the study. If this review suggests that assumed incidence used to plan the study is much higher than the actual event rate then we may reestimate the sample size to ensure the study is adequately powered. Since the analysis will be conducted blind to group assignment this will not introduce statistical bias and adjustment to the study's significance level is not required...

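### The interim sample-size rule in F5.5 is incomplete: it responds only to incidence below plan and does not say which effect scale is held fixed

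*Combined protocol and SAP*

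**What the plan says.** F5.5 describes one look: "A blinded review of the study's overall incidence of the primary study outcome and the primary safety endpoint will be planned after 50" per cent of patients have finished. The only action it names, a new sample-size calculation, is conditional and discretionary: "If this review suggests that assumed incidence used to plan the study is much higher than the actual event rate then we may reestimate". Assumed incidence above actual incidence means that the observed rate is below plan. The section says nothing about a rate above plan. It gives no number for the trigger, no ceiling on N, and no statement of which effect is carried into the new calculation.

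F.4 gives a "sample size of 504 patients" at a "two-sided overall 5% significance level with Bonferroni adjustment for multiple testing", which is 0.025 for each of two comparisons, and claims more than 80% power. The limiting comparison is set "to detect an absolute difference in in-hospital bleeding (Aim 1) between the low ACT target and the medium ACT target (ie. 5% vs. 15" per cent; the other is 5% vs 25%. F5.2 reports the Aim 1 effect as relative risks.

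For Aim 3, F3.4 sets a non-inferiority margin that depends on the estimated high-arm NACE proportion: 0.12 at or above 12%, equal to the estimate between 4% and 12%, and 0.04 at or below 4%. F.4 claims more than 80% power when the two arms have equal NACE rates and the high-arm rate is 12% or more. It cites a literature median of 12% and a range of 4% to 20%.

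**The concern.** The purpose of F5.5 is to keep the trial adequately powered if the planning rates prove wrong. Which direction of error costs power depends on what stays constant. If an absolute difference stays constant, variance grows as the rates move up towards 50%, and power falls when incidence is higher. If a ratio of risks stays constant, the absolute gap shrinks with the rates, and power falls when incidence is lower. F.4 is written on the first scale, the F5.5 trigger suits the second, and F5.2 reports on the second. The plan never says which one governs.

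At stake is the low-vs-medium comparison in Aim 1, which has almost no reserve at plan. If bleeding runs above plan with the 10-point gap intact, the review would see the cause of the lost power and the plan would prescribe no response. A null low-vs-medium result would then be hard to interpret. Aim 3 has the same gap on its high side.

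**Working it through.** **Inputs.** 504 patients, 1:1:1, so 504/3 = 168 per arm (F.4, F1). Two-sided 0.025 per comparison; chi-square test (F.4, F5.2). Planned bleeding 5%, 15% and 25%, so the planned pooled rate is (5+15+25)/3 = 15%. NACE margin from F3.4 and Newcombe interval from F5.2. The alternative incidence values below are assumptions shown as a range; the documents give no expected deviation.

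**1. Reproducing the plan.** Normal approximation per arm:

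n = [z(0.9875)·√(2p̄(1−p̄)) + z(0.80)·√(p₁(1−p₁)+p₂(1−p₂))]² / (p₂−p₁)²

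For 5% vs 15%, p̄ = 0.10: (2.2414×√0.18 + 0.8416×√0.175)² / 0.01 = (0.9510 + 0.3521)² / 0.01 = 169.8, so 170 per arm (510 in total, against 504). Exact binomial enumeration of the uncorrected chi-square test at 168 per arm gives 81.2% for low vs medium and 99.9% for low vs high. The stated figure reproduces. With Fisher's test, which F5.2 also allows, low vs medium is 76.4%.

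**2. Absolute gaps of 10 and 20 points held.** With low-arm rate L, the pooled rate is (L + L+10 + L+20)/3 = L+10. Exact power at 168 per arm, and n per arm for 80% power from the formula above:

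| Pooled | Low / medium / high | Low vs medium | Low vs high | n per arm (total) |
|---|---|---|---|---|
| 12% | 2 / 12 / 22 | 94.3% | above 99% | 123 (369) |
| 15% (plan) | 5 / 15 / 25 | 81.2% | 99.9% | 170 (510) |
| 17.5% | 7.5 / 17.5 / 27.5 | 71.5% | 99.8% | 207 (621) |
| 20% | 10 / 20 / 30 | 63.9% | 99.4% | 242 (726) |
| 25% | 15 / 25 / 35 | 52.6% | 98.1% | 303 (909) |

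For example, 10% vs 20%: (2.2414×√0.255 + 0.8416×√0.25)² / 0.01 = (1.1319 + 0.4208)² / 0.01 = 241.1, so 242.

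**3. Risk ratios of 3 and 5 held.** The direction reverses:

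| Pooled | Low / medium | Low vs medium | n per arm (total) |
|---|---|---|---|
| 22.5% | 7.5 / 22.5 | 95.8% | 107 (321) |
| 15% (plan) | 5 / 15 | 81.2% | 170 (510) |
| 12% | 4 / 12 | 69.4% | 218 (654) |
| 10% | 3.3 / 10 | 59.1% | 265 (795) |
| 7.5% | 2.5 / 7.5 | 43.5% | 360 (1080) |

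**4. A limit on the absolute scale.** From step 2, L = pooled − 10. Below a pooled rate of 10% L would be negative, so the 10- and 20-point gaps cannot both exist.

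**5. NACE non-inferiority.** Equal true rates in the low and high arms, 168 per arm, exact enumeration. The Newcombe upper limit is Δ_U = (p_L − p_H) + √[(u_L − p_L)² + (p_H − l_H)²], where u_L and l_H are Wilson 95% limits. It is compared with the F3.4 margin at the observed p_H:

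| NACE rate | 4% | 6% | 8% | 10% | 12% | 15% | 20% | 25% | 30% |
|---|---|---|---|---|---|---|---|---|---|
| Power | 47% | 55% | 66% | 74% | 81% | 84.5% | 79% | 73% | 68% |

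The F.4 figure reproduces at 12%. It does not hold at 20% or above. Below 12% the margin shrinks with the rate and power drops quickly.

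**The case against.** The strongest defence is that F5.5 chose a sensible direction. Relative risk is the effect measure reported for Aim 1, and under a stable ratio low incidence is the threat (step 3). Below 10% pooled bleeding the planned gaps are impossible on any reading (step 4). F5.5 also covers the safety endpoint, where a low rate costs most (step 5). All of this stands. A reader who sees the absolute wording in F.4 might infer that the existing trigger points the wrong way; the documents do not support that.

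A reader might also infer from Table 2 that bleeding will run high, since its lowest-ACT row (mean 147 s) reports 18% hematomas against 5% assumed for the low arm. That row is described as "Mostly diagnostic procedures, all radial cases, 5F sheaths, no high risk patients", and the other two hematoma rates are 3% and 5%. Section A cites bleeding in about 1 in 10 patients at recommended targets, below the planned pooled 15%. Definitions differ, as F.4 acknowledges. These sources do not settle the direction, which is a reason to cover both.

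Third, because F1 says "we will not conduct the study in a strictly blinded fashion", a reader might conclude that site staff would bias the review. The review uses pooled incidence, and nothing in the documents shows that knowledge of assignments would alter it.

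Finally, the text does not forbid action when incidence is high, and low vs high keeps its power. Both are true. Neither supplies a planned response for low vs medium.

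**Conclusion.** The rule is incomplete rather than misdirected. It covers one of two directions in which power can be lost, with no numerical trigger, no cap and no declared effect scale. On the scale F.4 uses, a rise in pooled bleeding from 15% to 20% costs about 17 points of low-vs-medium power (81.2% to 63.9%), and a rise to 25% costs about 29 (81.2% to 52.6%). For NACE, the claim of more than 80% power at 12% or more is not true throughout that range: it is 79% at 20%, which the protocol itself cites, and 73% at 25%.

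These sizes assume 168 per arm with no loss, the uncorrected chi-square test, gaps of exactly 10 and 20 points, and equal NACE rates in the low and high arms. If the risk ratio is what stays constant, higher bleeding incidence raises power and the existing trigger suffices for Aim 1. The documents do not say which holds, and they do not show that high incidence is the likelier case.

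**What to change.** Keep the low-incidence trigger in F5.5 and add a high-incidence one.

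- State the planned rates, 15% pooled bleeding and 12% NACE, with a numerical trigger on each side of each.
- State the effect scale held fixed: the 10-point absolute difference when pooled bleeding is above plan; the relative risk, or a restated detectable difference, when it is below. Holding 10 points in both directions would not do, because the required n then falls with incidence and the low-side protection disappears.
- Apply the rule to both endpoints, from pooled counts only, with a maximum N set in advance.
- If the trial is not enlarged, or the maximum binds, restate the low-vs-medium and NACE power at the observed pooled rates.
- Correct the F.4 statement on NACE power so that it gives the range of rates over which it holds.

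The cost is wording in F5.5 and one sentence in F.4. The downside is that a less favourable power figure may have to be reported. Enlarging the trial is a separate decision: on the absolute scale, 80% power for low vs medium needs about 621 patients at pooled 17.5% and 726 at 20%, which the maximum N must weigh against the accrual period in F.4.

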## Appendix I

### Bleeding Academic Research Consortium (BARC) Standard Bleeding Definition(26)

BARC 0	No bleeding
BARC 1	Non-actionable bleeding
BARC 2	Actionable bleeding, even if on imaging alone, that meets one of the following:1) requires non-surgical (medical) intervention by healthcare personnel; 2) leads to hospitalization or escalation in level of care; 3) prompts evaluation.
BARC 3a	Overt bleeding AND hemoglobin drop 3 to 5 g/dL OR blood transfusion
BARC 3b	Overt bleeding AND hemoglobin drop $\geq 5$ OR cardiac tamponade, bleeding requiring surgical intervention for control, need for intravenous vasopressor
BARC 3c	Intracranial/intraspinal hemorrhage or intraocular hemorrhage with any visual impairment
BARC 4	CABG-related bleeding
BARC 5	Probable or definite fatal bleeding

### EASY Hematoma Classification Scale

## Appendix II

### Optimal Target of Activated Clotting Time During Percutaneous Coronary Intervention and Outcomes: The OPTIMAL-ACT Trial

#### Study Endpoint Definitions:

##### Bleeding

-EASY hematoma classification after Transradial/Ulnar PCI

Type 1: less than 5cm in diameter from puncture site

Type 2: 5-10 cm in diameter from puncture site

Type 3: >10 cm in diameter but below the elbow limited to the forearm

Type 4:>10 cm in diameter and extends above the elbow

Type 5: any bleeding location with compartment syndrome (ischemic threat to the limb)

-BARC 2, 3, or 5 bleeding using BARC defined bleeding scale

BARC 0	No bleeding
BARC 1	Non-actionable bleeding
BARC 2	Actionable bleeding, even if on imaging alone, that meets one of the following:1) requires non-surgical (medical) intervention by healthcare personnel; 2) leads to hospitalization or escalation in level of care; 3) prompts evaluation.
BARC 3a	Overt bleeding AND hemoglobin drop 3 to 5 g/dL OR blood transfusion
BARC 3b	Overt bleeding AND hemoglobin drop $\geq 5$ OR cardiac tamponade, bleeding requiring surgical intervention for control, need for intravenous vasopressor
BARC 3c	Intracranial/intraspinal hemorrhage or intraocular hemorrhage with any visual impairment
BARC 4	CABG-related bleeding
BARC 5	Probable or definite fatal bleeding

Net Adverse Clinical Events (composite of all-cause mortality, myocardial infarction, stroke, target lesion revascularization, or bleeding)

Stent thrombosis (ST) :

Definite (ST): ACS with angiography or autopsy evidence of stent thrombosis.

Probable (ST): Unexplained death within 30 days of index procedure or acute myocardial infarction involving the target-vessel territory without angiographic confirmation.

Myocardial infarction: presence of 2 of the following: ischemic symptoms; elevation of cardiac troponin  $>99^{\text{th}}$  percentile of lab upper reference range with typical rise and fall; ECG changes compatible with infarction. For cardiac troponin elevated prior to PCI due to myocardial infarction, the subsequent troponin would need to be increased by 20% or more than the previous value to be considered an endpoint event.

Stroke: Focal loss of neurological function caused by an ischemic or hemorrhagic insult, with residual symptoms lasting at least 24 hours, and confirmed on neuroimaging (CT or MRI) with final impression deemed as stroke by a consulting neurologist

Target lesion revascularization: repeated PCI of the stented segment

Intra-procedural thrombus: visible filling defect noted by the operator on the guiding catheter or intracoronary wire or device during selective angiography with or without adjunctive confirmation on alternative coronary imaging modality (IVUS/OCT)

References:

3. Yusuf S, et al. Effects of clopidogrel in addition to aspirin in patients with acute coronary syndromes without ST-segment elevation. *N Engl J Med*. 2001;345:494-502.
